6.6 Treatment Verification

- 6.6.1 A radiation oncologist will be present for set-up verification and treatment delivery of every fraction.
- 6.6.2 Orthogonal isocenter verification films (or images) must be obtained prior to each treatment. For VMAT the intensity profiles of each beam must be independently verified and compared to the planned field intensity. These images are to be archived by the institution for later review if requested by the study chair.

Set-up on the treatment machine will be verified using kV-kV imaging and cone-beam CT with robotic couch to match anatomy in all translational and rotational discrepancies. ExacTrac imaging, kV-kV 2D/3D matching, or repeat cone-beam CT will be used between each rotational arc of radiation treatment to ensure stability of set-up and make ongoing set-up adjustments.

The CyberKnife Treatment Delivery System uses kV orthogonal X-ray imaging for live motion tracking to ensure stability of set-up and for motion correction throughout treatment.

6.6.3 Management of Radiation Dose to the Patient from Daily Localization

According to the literature, the estimates of patient dose per imaging study for various imaging systems vary considerably. The doses are in the range of 0.1 cGy for BrainLab's ExacTrac planar kV-systems and can be considered negligible compared with doses from MV portal imaging and kV and MV CT. The doses from CyberKnife kV X-ray imaging is estimated to be in the range of 0.025-0.2 cGy. The doses from helical MV CT scans on a tomotherapy unit are estimated to be in the range of 1 to 3 cGy, similar to doses reported for kV cone beam CT on the Elekta Synergy machine. The doses for MV cone beam CT vary from 1 cGy to 10 cGy depending on the field size. Thus, the doses for 3D imaging systems used one time each day are in the range of 0.1 to 10 cGy and can contribute from 0.06 to 6% to a daily dose of 1.8 Gy. As a technique of controlling participant dose, it is recommended that a QA procedure be established at each participating institution to verify the accuracy of the image registration software on a daily basis. This QA check should be performed by the therapists operating a particular treatment device and is aimed at reducing the use of repeat imaging to check that the registration software has functioned properly when a shift of participant position is carried out. Additionally, it is not recommended that an institution use a daily imaging technique that delivers greater than 3cGy/day to the patient. This limit dictates that repeat imaging on a particular day is held to a minimum when systems that deliver up to 3 cGy per study are used.

6.7 Quality Assurance

6.7.1 Radiation Documentation Requirements

The institution will archive treatment prescription and verification images for later review by the study chair if requested. At least one port film or pretreatment alignment film per field along with the digitally reconstructed radiographs (DRRs) from the treatment planning program or, alternatively, a simulation verification radiograph shall be acquired and kept for evaluation if requested except where geometrically impractical. For CyberKnife SBRT, a screenshot of the alignment of the day of treatment X-Ray (Camera Image) to the DRR (Synthetic Image) will be acquired and kept for evaluation if requested.

6.7.2 Compliance Criteria

Cases which meet criteria as stated in Section 6.1.2 will be scored as per protocol.

The minimum allowable dose within the PTV is >80% of the prescribed dose to a volume that is at least 1 cc. Cases in which this small volume of at least 1 cc receives a minimum dose that is <80% but >75% will be scored as a “deviation acceptable”.

Cases in which 1 cc receives less than 75% of the prescribed dose will be scored as a “deviation unacceptable”. However, if this is what is required to keep the spinal cord or cauda equina within the maximum dose constraint, as specified above, this variation is considered “deviation acceptable”.

6.7.2.1 Acceptable dose heterogeneity will be as follows: The maximum dose volume of the PTV must not be shared by a normal critical structure. (Section 6.4.1.5). The maximum point dose to normal critical structures outside the PTV including the unspecified tissue should not exceed dose specified in Table 1. The treating physician must carefully consider the tolerance dose/volume to each critical normal structure and unspecified tissue.

6.8 Radiation Quality Assurance Reviews

RT quality assurance reviews will be ongoing and performed by the co-investigators and will be reviewed by the PI.

6.9 Radiation Adverse Events

6.9.1 All participants will be seen weekly by their treating radiation oncologist while undergoing therapy. The specific symptoms/side effects to be assessed will depend on the area(s) of the body undergoing treatment. A comprehensive list is below (see section 6.9.2); however every patient will not be assessed for every symptom if it is not relevant to the site(s) being treated.

Every patient will be assessed for:

- Pain – at the site(s) being treated
- Pain – at other locations
- Tiredness
- Skin reddening or irritation

- Skin peeling
- Nausea/Vomiting
- Hair loss

6.9.2 Comprehensive list of possible toxicities. The anticipated toxicity for each individual patient is very dependent on the location and the anticipated toxicities will be discussed in detail with the patient. These are listed in both the standard consent form the patient will sign for radiation treatment and the protocol-specific consent form as well as below.

Short Term Reactions (Appearing during radiation therapy or within 1 month thereafter; temporary, generally resolving within 2-3 months):

Common (> 20%):

- Tiredness
- Skin reddening & irritation that is reversible
- Loss of hair in the area of treatment
- Loss of taste
- Mild sore throat and difficulty swallowing
- Decreased blood counts that are reversible
- Weight loss that is reversible
- Pain flare

Rare (< 5%):

- Nausea
- Diarrhea
- Bladder irritation
- Fever and chills (within the first few hours of radiation)
- Severe esophagitis

Long Term Reactions (Appearing months after radiation; permanent, does not resolve)

Uncommon (10-20%):

- Mild scarring of skin or muscle without changes in function
- Mild scarring of the lung not requiring treatment
- Bone fractures

Rare (< 5%):

- Loss of hair in the treatment area
- Damage to spinal cord or nerves resulting in pain or other sensory changes
- Damage to spinal cord or nerves resulting in loss of motor function

- Damage to the esophagus limiting function

Extremely Rare ($\leq 1\%$):

- Tumors caused by radiation
- Damage to bone or muscle limiting function
- Sterility
- Damage to the heart

6.10 Radiation Adverse Event Reporting

All adverse event reporting requirements are found in Appendix C.

6.11 Toxicity Assessment and Management

Any observations with respect to symptoms or side effects that are possibly, probably, or definitely related to SBRT treatment will be followed for AE reporting.

7. DRUG THERAPY

N/A – No medications will be given as part of this study. Medications for pain relief or other reasons may be given at the discretion of the treating physician and are covered in Section 9 below.

8. SURGERY

Surgery to the metastatic site(s) is allowed, but is not required, prior to enrollment on this study. The study does not include any surgical procedures.

9. OTHER THERAPIES

The following may be given at the discretion of the treating radiation oncologist:

- Dexamethasone – to be taken pre-treatment to prevent pain flare
- Benzodiazepines – as needed for anxiety during the SBRT planning and/or treatment
- Pain medications – as needed to control pain and allow the patient to be comfortable while undergoing treatment

10. TISSUE/SPECIMEN SUBMISSION

N/A: No tissue or specimens will be collected as part of this study nor will any previously collected tissue or specimens be used in any way as part of this study.

11. PARTICIPANT ASSESSMENTS

11.1 Definitions

- 11.1.1 Target Lesion(s) – Spine or non-spine bone metastatic site(s) being treated with SBRT. Up to a total of 3 lesions, as per the inclusion criteria. These will be recorded and measured at baseline. A sum of the longest diameter (LD) for all target lesions will be calculated and reported as the baseline sum LD. The baseline sum LD will be used as the reference by which to characterize the objective tumor response.
- 11.1.2 Non-Target Lesion(s) – Any other lesions, either sites of stable disease or sites that have been or will be treated with other modalities than SBRT. Presence or absence of these lesions will be determined at the discretion of the treating radiation oncologist in collaboration with other treating physicians.

11.2 Methods/Requirements for assessments

- 11.2.1 Target Lesion(s): Will be evaluated via CT and/or MRI at the discretion of the treating physician. The same diagnostic modality(ies) will be used for assessment at each of the specified time points. A diagnostic radiologist reading the scan will be asked to measure the lesion(s) in the largest dimensions.
- 11.2.2 Non-Target Lesion(s): Will be evaluated via CT, PET/CT, and/or MRI at the discretion of the treating physician.

11.2.3 Toxicity Assessment

Toxicity assessments will be done using the CTEP Active Version of the NCI Common Terminology Criteria for Adverse Events (CTCAE) which is identified and located on the CTEP website at:

http://ctep.cancer.gov/protocolDevelopment/electronic_applications/ctc.htm.

11.2.4 QOL Assessment

QOL Assessment will be done using a modified MD Anderson Symptom Inventory (see Appendices D, E, F, and G), which is a validated questionnaire. The modified version to be used includes MDASI core questions, a spinal symptom inventory, and additional items pertinent to radiation therapy for palliation of bone metastases and pain.

11.2.5 Timing of Assessments

Baseline assessments will be done for the target lesion, non-target lesion(s), pre-existing toxicity and QOL. Participants' first assessment post-treatment will occur at 1 week (\pm 3 days) to assess for QOL. Participants will then undergo another evaluation at 1 month (\pm 1

week) to assess for QOL. Participants will then be evaluated at 3 months (\pm 4 weeks) with imaging (CT or MRI as per treating physician) done at the time of follow-up (\pm 2 weeks). Participants will then be evaluated at 6 months (\pm 2 months) and every 6 months thereafter through year 2 (\pm 3 months) and annually years 3-5 (\pm 6 months), with imaging (CT or MRI as per treating physician) done at the time of follow-up (\pm 2 weeks). We will attempt to coordinate all visits and scans with the patient's other medical providers to avoid duplicate visits or scans and minimize inconvenience to the patient and protocol violations. Please see Appendix B for additional study parameters.

	Pre-Study	Treatment	Week 1 ^b	Month 1 ^c	Month 3 ^d	Month 6 ^e	Every 6 months after month 6 through year 2 ^f	Annually Years 3-5 ^g
Target Lesion(s)	X				X	X	X	X
Toxicity Assessment	X	X ^h			X	X	X	X
QOL Assessment	X	X ^a	X	X	X	X	X	X

a: On mid-point and last day of radiation

b: \pm 3 days

c: \pm 1 week

d: \pm 4 weeks

e: \pm 2 months

f: \pm 3 months

g: \pm 6 months

h: During on treatment visit

Note: The baseline “pre-study” questionnaire can be given anytime between the initial consult appointment and the first radiation therapy treatment, as long as the patient has not yet received radiation

Note: Imaging will be done at clinicians' discretion.

Participants will be given the option on each survey to decline.

Administration of questionnaires will be determined, as follows, by the time of follow-up.

Questionnaire Version	Timeline	Appendix Reference
Symptom and Pain Baseline Assessment	Prior to initial RT	Appendix D
Symptom and Pain Assessment in the Past 24 Hours	Mid-point and on last day of treatment	Appendix E
Symptom and Pain Assessment in the Past 7 Days	1 week and 4 week follow-up	Appendix F
Symptom and Pain Assessment, Long-Term Follow-Up	3 months, every 6 months for 2 years, and annually from years 3 to 5	Appendix G

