12.2 Additional Data Collection

	Maximum Time to Data Collection					
	Prior to 1st treatment	Within 1 Week after completion of treatment	2 weeks after completion of treatment	5 Weeks after completion of Treatment	4 Months after completion of treatment	10 months after completion of treatment, every 6-9 months through year 2, then annually through year 5
Informed Consent	X					
History	X					
Medication Review	X	X			X	X
Physical exam (Ht, Wt, VS)	X					
Performance Status	X	X			X	X
Pre-existing condition or Adverse event evaluation	X	X			X	X
Tumor measurements	X				X	X
Radiologic evaluation	X				X	X
B-HCG*	X					
QoL questionnaire	X	X	X	X	X	X
Other malignancy related treatments undergone since last visit					X	X
SBRT GTV, CTV, PTV (as applicable) Dose Volume Information		X				
Critical Normal Tissue Dose Volume Data		X				

Treatment Delivery Information		X				
--------------------------------	--	---	--	--	--	--

**For pre-menopausal women for whom pregnancy is a possibility (i.e., have not undergone a hysterectomy)*

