APPENDIX B STUDY PARAMETERS

Assessments	Pre-Study	Simulation	Radiation Treatment	Follow-Up ⁽¹⁾
Informed Consent and Registration	X			
History/physical/vital signs	X			X
Performance Status	X			X
Pregnancy Test (B-HCG)	X			
Diagnostic CT or MRI (at discretion of treating physician)		X ⁽²⁾		
Imaging study (CT or MRI to be determined by treating physician)				X ⁽³⁾
Toxicity Assessment	X		X ⁽⁶⁾	X
QOL questionnaire	X		X ⁽⁴⁾	X ⁽⁵⁾

- (1) Follow up schedule: initial evaluation at 1 week after completion of radiation therapy (via telephone, in person or email), then at 1 month after completion (via telephone, in person or email), 3 months, 6 months and every 6 months thereafter through year 2 (in person, telephone or email), then annually through year 5. Visits can be scheduled within a pre-specified time window around the anticipated date.
- (2) Baseline imaging is to be done within 21 days of start of first fraction of radiation
- (3) Follow up imaging is to be done within 2 weeks before or after scheduled follow up visit.
- (4) On mid-point and last day of radiation
- (5) QOL questionnaire to be completed within 2 weeks of follow up visit.
- (6) During on treatment visit

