- emergency outpatient treatment for an event not fulfilling the serious criteria outlined above and not resulting in inpatient admission
- respite care

Expectedness: Adverse events can be 'Expected' or 'Unexpected.'

- Expected adverse event
 - Expected adverse events are those that have been previously identified as resulting from administration of the agent. For the purposes of this study, an adverse event is considered expected when it appears in the current adverse event list or is included in the informed consent document as a potential risk.
 - Refer to Section 6.9 for a listing of expected adverse events associated with the study agent.
- Unexpected adverse event
 - For the purposes of this study, an adverse event is considered unexpected when it varies in nature, intensity or frequency from information provided in the current adverse event list or when it is not included in the informed consent document as a potential risk.

Attribution

- Attribution is the relationship between an adverse event or serious adverse event and the study treatment. Attribution will be assigned as follows:
 - Definite – The AE is clearly related to the study treatment.
 - Probable – The AE is likely related to the study treatment.
 - Possible – The AE may be related to the study treatment.
 - Unlikely - The AE is doubtfully related to the study treatment.
 - Unrelated - The AE is clearly NOT related to the study treatment.

PROCEDURES FOR AE AND SAE RECORDING AND REPORTING

Investigators will assess the occurrence of AEs and SAEs at all participant evaluation time points during the study.

All AEs and SAEs whether reported by the participant, discovered during questioning, directly observed, or detected by physical examination, laboratory test or other means, will be recorded in the participant's medical record and on the appropriate study-specific case report forms.

The descriptions and grading scales found in the CTEP Active Version of the NCI Common Terminology Criteria for Adverse Events (CTCAE) will be utilized for AE reporting. The CTEP Active Version of the CTCAE is identified and located on the CTEP website at:

http://ctep.cancer.gov/protocolDevelopment/electronic_applications/ctc.htm.

All appropriate treatment areas should have access to a copy of the CTEP Active Version of CTCAE.

ADVERSE EVENT REPORTING REQUIREMENTS

Serious Adverse Event Reporting

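### The 11.2.5 and 12.2 schedules leave toxicity grading unmarked at Week 1 and Month 1 although Appendix C wants adverse events assessed at every evaluation, so expected, non-serious acute reactions may be under-counted.

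*Combined protocol and SAP*

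**What the plan says.** - **11.2.5, text.** A participant's "first assessment post-treatment will occur at 1 week (\pm 3 days) to assess for QOL". The next sentence begins "Participants will then undergo another evaluation at 1 month" and again names QOL as the purpose. The section then sends the reader on: "Please see Appendix B for additional study parameters".
- **11.2.5, table.** Toxicity Assessment is marked pre-study, on treatment, and from Month 3 onward. The Week 1 and Month 1 cells are blank.
- **12.2, table.** The row "Pre-existing condition or Adverse event evaluation" is marked before treatment, in the column "Within 1 Week after completion of treatment", at 4 months and later. It is blank at 2 weeks and at 5 weeks.
- **Appendix B.** Toxicity is marked in a single pooled Follow-Up column. Note 1 defines follow-up as "initial evaluation at 1 week after completion of radiation therapy (via telephone, in person or email), then at 1 month after completion", and then the later visits.
- **Appendix C.** "Investigators will assess the occurrence of AEs and SAEs at all participant evaluation time points during the study". Section 6.10 names this appendix as the place for adverse event reporting requirements.
- **6.9.2.** Short-term reactions are those that arise during treatment or in the month after it. They are said to resolve, as a rule, in 2 to 3 months.
- **2.3 and 13.6.** The acute toxicity rate is a secondary objective and will be reported.

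**The concern.** The protocol calls both early contacts evaluations: 11.2.5 does so for month 1, and Appendix B note 1 for week 1. Appendix C therefore applies to them, yet the two tables that staff are most likely to work from mark no toxicity assessment there. The blanks fall in the month in which the protocol's own definition places acute reactions.

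At stake is the reported acute toxicity rate. An expected, non-serious reaction that begins after the last treatment-related check and settles before month 3 has no scheduled clinician grading under those tables. If some staff follow Appendix C and others follow the tables, the rate also depends on which section was followed. The on-treatment visit covers little of the window. Regimens are 1, 3 or 5 fractions (6.1.1) and visits are weekly during therapy (6.9.1), so for a single fraction that visit falls on the treatment day.

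**Working it through.** **The plan's own figure.** The only stated figure that depends on capturing toxicities is in 13.6: the chance of seeing at least one event at a true rate of 5%. With n = 100 and n = 50 (13.2):

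- Cohort 1: 1 − 0.95^100 = 0.9941, stated as 99.4%.
- Cohort 2: 1 − 0.95^50 = 0.9231, stated as 92.3%.

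Both reproduce. Both take it that every event is recorded.

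**The schedules side by side.**

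| Source | Week 1 | Month 1 | Month 3 |
|---|---|---|---|
| 11.2.5 table, toxicity | blank | blank | marked |
| 11.2.5 table, QOL | marked | marked | marked |
| 12.2, adverse event row | blank (2-week column) | blank (5-week column) | marked (4-month column) |
| Appendix B, toxicity | pooled mark | pooled mark | pooled mark |
| Appendix C | required | required | required |

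The QOL row is filled in all eight columns of the 11.2.5 table, so the toxicity blanks are not a column shift. The 12.2 columns are latest collection times and match the visit windows: 7 + 3 = 10 days falls within 2 weeks, 1 month + 1 week is about 5 weeks, and 3 months + 4 weeks is about 4 months. The within-1-week column also holds the dose-volume and treatment delivery data, so it reads as the end-of-treatment deadline.

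**Timing.** Assume 1 month = 30 days, 2 months = 61 and 3 months = 91, counted from completion of treatment.

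- Week 1: 7 ± 3 = days 4 to 10.
- Month 1: 30 ± 7 = days 23 to 37.
- Month 3: 91 ± 28 = days 63 to 119.
- Delay after the onset window closes at day 30: 63 − 30 = 33 days to 119 − 30 = 89 days.

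Scheduled CTCAE gradings after treatment and before day 63: none in the 11.2.5 table, at most one end-of-treatment check in 12.2, and two more if both contacts are marked. Those two fall inside the window or at its edge.

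**Have reactions resolved by month 3?** Section 6.9.2 does not say where its 2 to 3 months start.

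- From completion: about days 61 to 91. The nominal visit (day 91) is at the end of that range.
- From onset, for a reaction starting on day 30: 30 + 61 = day 91 to 30 + 91 = day 121. The nominal visit is then at the start of that range.

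**Illustration only.** Let s be the share of true events recorded. The documents give no value for s. The recorded rate is s times the true rate, and the 13.6 probability becomes 1 − (1 − 0.05s)^n.

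| Assumed s | Recorded rate if truth is 20% | Cohort 1 | Cohort 2 |
|---|---|---|---|
| 1.0 | 20% | 99.4% | 92.3% |
| 0.8 | 16% | 98.3% | 87.0% |
| 0.5 | 10% | 92.0% | 71.8% |

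This shows the direction of the effect, not an estimate of it.

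**The case against.** The case on the other side has force on several points.

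- **Appendix B.** A reader might infer that it plainly requires toxicity assessment at both contacts. It does not. The same pooled column marks physical examination and imaging without limit, and nobody would read that as a scan at a contact that may be by email. The column is a summary and only weak support. The conflict rests on Appendix C.
- **Which section governs.** A reader might infer that staff have no way to tell. That is too strong, because 6.10 points to Appendix C for reporting requirements, and Appendix C applies alongside 11.2.5. What remains is that two working tables do not show the duty.
- **The 11.2.5 text.** It names no toxicity assessment at month 3 either, so its silence does not exclude one. The tables carry the point.
- **Resolution.** A reader might infer that acute reactions will usually be gone by month 3. The documents support that only if the 2 to 3 months run from completion. Some reactions may still be present or recalled.
- **Other capture.** Appendix F, used at both contacts, asks about fatigue, nausea, vomiting, swallowing, diarrhea and treated-site pain, and about medicines started or increased. SAEs, and unexpected Grade 2–3 events at least possibly related, are reportable within 30 days. Events that participants report must be recorded.

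These routes narrow the gap but do not close it. Appendix F scores are not CTCAE grades, there is no skin or hair item, and "Participants will be given the option on each survey to decline". The month 3 form (Appendix G) asks about symptoms in the last 24 hours. Recording what a participant volunteers is not scheduled assessment.

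**Conclusion.** The conflict is real and limited. The 11.2.5 and 12.2 tables mark no toxicity assessment at two contacts where Appendix C requires one. If staff follow the tables, nothing is graded on schedule between an end-of-treatment check and about days 63 to 119, which is 33 to 89 days after the onset window closes. Expected, non-serious acute reactions may be under-counted, or counted unevenly.

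The day counts rest on the month lengths assumed above and on counting from completion. Whether reactions have gone by month 3 depends on an unstated starting point in 6.9.2. The size of any bias cannot be derived.

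A reader might infer that safety reporting is compromised. The documents do not support that, because serious events and unexpected, at least possibly related Grade 2–3 events have their own 30-day route. The primary endpoint is unaffected. Severity is minor to moderate: one descriptive secondary endpoint.

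**What to change.** Reconcile 11.2.5 and 12.2 with Appendix C:

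1. In the 11.2.5 text, add toxicity to the stated purpose of the week 1 and month 1 contacts.
2. In the 11.2.5 table, mark Toxicity Assessment (CTCAE) at Week 1 and Month 1.
3. In 12.2, mark the adverse event row in the 2-week and 5-week columns.
4. In Appendix B note 1, state which Follow-Up items apply at these two contacts, including toxicity.

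The cost is two sentences, a few table marks and one note, plus a few minutes at each of two contacts already planned. A short call is needed where the contact would have been by email, and there is some added data entry. Skin findings would rest on self-report at remote contacts. The change adds nothing on blood counts, since none is scheduled.

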13. STATISTICAL CONSIDERATIONS

13.1 Study Design/Primary Endpoint

The primary objective of this study is to evaluate the 6-month local control rate of SBRT. The 6-month local control rate is the proportion of patients free of local failure at 6 months. Local failure is defined as the presence of biopsy-proven recurrence or radiologic scans that demonstrate progression at the treated sites.

Two cohorts of patients will be enrolled. Cohort 1 is comprised of patients with oligometastatic disease defined as ≤ 3 active sites of disease, including the primary site. Cohort 2 comprises patients who require re-irradiation of spinal disease. The primary analysis includes eligible and treated patients from both cohorts evaluated separately.

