13.2 Sample Size, Accrual Rate and Study Duration

We planned to enroll a total of 100 patients, 50 per cohort, into this study in the original design. As the accrual was rapid and about half of the patients were prostate cancer patients in cohort 1, the sample size for cohort 1 was increased from 50 to 100 to allow patients with other histologies to participate in this trial.

The primary endpoint is local control rate at 6 months. Assuming a cumulative incidence of local failure at 6 months is 10%, the 6-month local control rate is 90% with 90% exact binomial confidence intervals of [83.6%, 94.5%] and [80.1%, 96.0%] for cohorts 1 and 2, respectively. The confidence intervals are narrow enough to provide a precise estimate local control rate. With the sample size increase in cohort 1, we can also estimate the local control rates with better precision for the subsets of patients with either prostate cancer or other histologies. To be conservative, unevaluable patients (patients without valid assessments demonstrating free of local failure at 6 months) will be considered as failures in the analysis although we do not

anticipate many unevaluable patients on this study.

Approximately 250 patients per year are treated with conventional external beam radiation therapy for bone metastases in our department, with approximately one third being spine metastases. We estimate that approximately 10% of those 250 would be eligible for this study, yielding about 2 patients per month. Additionally, we are currently treating an average of 4 patients per month with SBRT for spinal metastases (75% eligible for cohort 1 and 25% eligible for cohort 2). It is expected that 70% of these patients will participate. Hence, we anticipate to accrue 3 and 1-2 patients per month for cohorts 1 and 2, respectively, and the accrual will be completed, in total for both cohorts, over about 3 years.

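### An unqualified note leaving imaging to clinicians' discretion conflicts with the imaging schedule and can be read as making the 6-month scan optional, while patients without a valid 6-month assessment count as failures

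*Combined protocol and SAP*

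**What the plan says.** The primary endpoint is defined in section 13.1: "The 6-month local control rate is the proportion of patients free of local failure at 6 months". The same section adds: "Local failure is defined as the presence of biopsy-proven recurrence or radiologic scans that demonstrate progression at the treated sites". Section 11.3.2 gives an equivalent definition of local failure, with local control as its absence.

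The imaging schedule appears in several places:

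- Section 11.2.5 sets evaluations at 3 months, at 6 months (window ±2 months) and later, "with imaging (CT or MRI as per treating physician) done at the time of follow-up", with ±2 weeks for the scan. Its table marks target-lesion assessment at months 3 and 6.
- Section 11.2.1 says of target lesions: "Will be evaluated via CT and/or MRI at the discretion of the treating physician". It also asks for the same modality at every specified time point.
- Appendix B, footnote 3: "Follow up imaging is to be done within 2 weeks before or after scheduled follow up visit".
- Section 12.2 lists radiologic evaluation and tumor measurements among the follow-up data.

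Under the 11.2.5 table stands a one-line note, "Note: Imaging will be done at", which ends by naming the clinicians' discretion. It mentions neither modality, visit nor lesion type.

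Section 13.2 defines unevaluable patients as "patients without valid assessments demonstrating free of local failure at 6 months", treats them as failures as a declared conservative choice, and expects few of them. Section 13.5 says the resulting point estimate will inform the design of future studies.

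**The concern.** Everywhere else that target-lesion imaging is left to the physician, the text names CT or MRI, so the discretion concerns modality. The note is the exception. Read literally, it leaves open whether to scan at all, which conflicts with the schedule above it and with Appendix B.

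The conflict reaches the primary endpoint because freedom from local failure in practice has to be shown by imaging. A clinician who relies on the note and does not scan a well patient around month 6 may leave that patient without a valid assessment, and section 13.2 then scores a failure. It would be unclear whether a deviation had occurred. Appendix B, footnote 1, also appears to allow the 6-month contact by telephone or email, so an in-person visit need not prompt the scan.

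This is a single-arm estimation study with no comparison group to absorb such a shift. A reported rate that mixes true local failure with decisions not to scan is harder to use for planning.

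**Working it through.** **Inputs.** From section 13.2: assumed 6-month local failure 10%, so control 90%; cohort 1 n = 100; cohort 2 n = 50; 90% exact binomial intervals; unevaluable patients counted as failures. The documents give no proportion without a valid 6-month assessment. That proportion, *m*, is therefore an assumption, shown here at 5%, 10% and 20%.

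**Further assumptions.** Being unassessed is unrelated to outcome, and an unassessed patient has no other valid assessment that shows freedom from failure at 6 months.

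**Step 1: reproduce the plan's intervals.** The two-sided 90% Clopper-Pearson interval for x controlled of n runs from the 5% quantile of Beta(x, n − x + 1) to the 95% quantile of Beta(x + 1, n − x).

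- 90/100 gives 83.6% to 94.5%.
- 45/50 gives 80.1% to 96.0%.

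Both match section 13.2, so the plan's precision figures are correct when every patient is assessed.

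**Step 2: expected reported rate.** With unassessed patients scored as failures, the expected rate is 0.90 × (1 − m):

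- m = 5%: 0.90 × 0.95 = 85.5%
- m = 10%: 0.90 × 0.90 = 81%
- m = 20%: 0.90 × 0.80 = 72%

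**Step 3: intervals, with counts rounded to whole patients.**

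| Unassessed | Cohort 1 | 90% interval | Cohort 2 | 90% interval |
|---|---|---|---|---|
| 0% | 90/100 | 83.6% to 94.5% | 45/50 | 80.1% to 96.0% |
| 5% | 86/100 | 79.0% to 91.3% | 43/50 | 75.3% to 93.2% |
| 10% | 81/100 | 73.4% to 87.2% | 40/50 | 68.4% to 88.7% |
| 20% | 72/100 | 63.7% to 79.3% | 36/50 | 59.7% to 82.2% |

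At 5% the cohort 1 expectation of 85.5 is rounded up to 86. Rounding down to 85/100 gives 77.8% to 90.5%, which also contains 90%.

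**Step 4: where the interval falls below 90%.**

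- Cohort 1: with 7 unassessed, 0.90 × 93 = 83.7, or 84/100. The interval is 76.7% to 89.7%, wholly below 90%.
- Cohort 2: with 5 unassessed, 0.90 × 45 = 40.5. Rounded to 40/50, the interval is 68.4% to 88.7%, below 90%; rounded to 41/50, its upper limit is 90.3%. With 6 unassessed, 0.90 × 44 = 39.6, again 40/50. The threshold is therefore about 5 to 6 patients.

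Under these assumptions the rate among assessed patients stays at about 90% throughout (for example 81/90), so the whole shift comes from the unassessed.

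**The case against.** The strongest reply is that the note is one more loose repetition of the modality choice. The protocol repeats itself often, and four places treat follow-up imaging as expected: the 11.2.5 text and table, section 11.2.1, section 12.2 and Appendix B, footnote 3. Section 11.2.5 also says visits and scans will be coordinated partly to reduce protocol violations, which suggests that a missed scan would be regarded as one. This stands as a plausible account of the intent. A reader might infer that the note cancels the scheduled scans. The documents do not support that; they support only that the note, as worded, makes the scans' status unclear.

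A reader might also infer that every skipped month-6 scan becomes a failure. Section 13.2 does not say that. It requires a valid assessment showing freedom from failure at 6 months, the visit window is ±2 months, and a later scan without progression could arguably serve. The calculation therefore applies only to patients with no such assessment. Assessments missed through death or refusal would be missing whatever the note says, so its own contribution cannot be separated out.

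The 5%, 10% and 20% rates have no source in the documents, section 13.2 expects few unevaluable patients, and at 5% the interval still contains 90% in both cohorts. Counting missing as failure is an openly conservative choice, so its direction is disclosed. These points limit the size of the problem but do not settle what the note means.

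A further tempting inference is that local progression-free survival is biased upward because silent progression goes unseen. That would follow only if scans were ordered mainly for symptoms, which the documents do not say. Section 13.6 also censors patients without documented progression at their last disease assessment, which reduces such a bias without removing it. It cannot be quantified from the documents.

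**Conclusion.** The point holds as an inconsistency with a possible effect on the primary estimate. The note conflicts with the schedule in its own section and with Appendix B, and can be read as making the 6-month target-lesion scan non-binding. Combined with the failure rule in section 13.2, that reading would let the primary rate partly reflect scan ordering.

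Under the stated assumptions the loss is 0.9 percentage points for each 1% of patients left unassessed. In cohort 1, about 7 unassessed patients of 100 are enough to put the interval wholly below the assumed 90%; in cohort 2, about 5 to 6 of 50. The documents do not show that scans will be skipped, so this is a sensitivity range and not a forecast. The plan's own intervals are arithmetically correct. Only the 6-month assessment drives the failure rule; a missed 3-month scan alone does not. Correcting the note is a cheap improvement.

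**What to change.** Reconcile the note with section 11.2.5 and Appendix B, footnote 3:

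- Limit the discretion in the note to the choice of CT or MRI.
- State that the 6-month target-lesion imaging already in the schedule is needed for the primary endpoint.
- Record a missed 6-month assessment in a living patient as a deviation, with its reason.

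The failure rule in section 13.2 can stay as it is. Recorded reasons would let readers see how much of any shortfall comes from missing assessments. The wording change is about one sentence and adds no scan beyond the existing schedule. The downside is that more deviations may be logged.
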